5.4 Efficacy Analyses

The FAS will be used as the primary population for the efficacy analyses. Due to the early termination of the study, only summary of descriptive statistics will be presented for efficacy variables.

5.4.1 Primary Efficacy Analyses

Due to the early termination of the study, only summary of descriptive statistics will be presented.

Multiple Imputation

No multiple imputation will be performed.

5.4.1.2 Sensitivity Analysis

There will be no sensitivity analyses due to the early termination of the study.

5.4.1.3 Subgroup Analysis

Due to the early termination of the study, the analysis of following planned subgroups will not be performed:

- age group
- sex (male and female)
- race (white, black, Asian and other)
- BMI group

5.4.2 Key Secondary Efficacy Analyses

Due to the early termination of the study, only summary of descriptive statistics will be presented.

5.4.3 Other Secondary Efficacy Analyses

The following efficacy analyses are for exploratory purpose only. For each efficacy endpoint specified below, only basic summary of descriptive statistics will be presented.

- 5.4.3.1 Proportion of subjects achieving at least a 5% BMI reduction at Week 12
- 5.4.3.2 Proportion of subjects achieving at least a 10% BMI reduction at Week 52
- 5.4.3.3 Percent change in BMI from baseline at Week 52
- 5.4.3.4 Change and percentage change in BMI from Baseline to Week 52 by the outcome of achieving at least a 5% BMI reduction at Week 12
- 5.4.3.5 Proportion of subjects achieving at least a 5% BMI reduction at Week 52 by the outcome of achieving at least a 5% BMI reduction at Week 12
- 5.4.3.6 Proportion of subjects achieving at least a 10% BMI reduction at Week 52 by the outcome of achieving at least a 5% BMI reduction at Week 12

5.5 Pharmacokinetic, Pharmacodynamics, Pharmacogenomics, and Other Biomarker Analyses

The methodology for these analyses will not be included in this SAP but will be described in a separate analysis plan if deemed necessary.

5.5.1 Pharmacokinetic Analyses

Lorcaserin plasma concentration-time data will be summarized.

5.5.2 Pharmacodynamics, and Other Biomarker Analyses

No PK analysis will be performed. Only lorcaserin plasma concentration-time data will be summarized.

5.6 Safety Analyses

Evaluations of safety will be performed on the Safety Analysis Set. Safety assessments including the incidence of AEs (including changes from baseline in physical examination, neuromuscular sign assessment, and signs and symptoms of priapism and hyperprolactinemia), out-of-normal-range laboratory safety test values, and change from baseline in laboratory safety test values, ECGs, and vital sign measurements will be summarized by treatment group using descriptive statistics or frequency count as appropriate. No hypothesis testing will be performed for the safety assessment. Study Day 1 for all safety analyses will be defined as the date of the 1st dose of study drug. All safety analyses should be based on “as treated” groups.

5.6.1 Extent of Exposure

Subjects will receive Belviq XR 20 mg or placebo QD for up to 52 weeks. The extent of exposure will be characterized by duration of exposure (in weeks) for each treatment group. Duration of exposure will be defined as the number of weeks between the date the subject received the 1st dose of study drug and the date the subject received the last dose of study drug. Duration of exposure will be summarized using descriptive statistics by treatment group. In addition, the duration of exposure will be categorized and will be summarized using frequency count by treatment group.

5.6.2 Adverse Events

A treatment-emergent AE (TEAE) is defined as an AE that emerges during treatment (up to 28 days after the last dose of study drug), having been absent at pretreatment (Baseline) or

- Reemerges during treatment (up to 28 days after the last dose of study drug), having been present at pretreatment (Baseline) but stopped before treatment, or
- Worsens in severity during treatment relative to the pretreatment state, when the AE is continuous.

Only those AEs that were treatment emergent will be included in summary tables. All AEs, treatment emergent or otherwise, will be presented in subject data listings.

The TEAEs will be summarized by treatment group. The following summaries will be reported for TEAES:

- Incidence of TEAEs in descending order of frequency
- Incidence of TEAEs by SOC and PT
- Incidence of treatment-related TEAEs by SOC and PT
- Incidence of TEAEs by SOC, PT and maximum severity (mild, moderate, or severe)
- Incidence of treatment-related TEAEs by SOC, PT, and maximum severity (mild, moderate, or severe)

Incidence of TEAEs by SOC, PT, and relationship to study drug (Yes [related] or No [not related])

A subject will be counted only once within a SOC or PT, if the subject experienced more than 1 TEAE within a specified SOC and PT.

The following summaries will also be presented for the treatment-emergent SAEs.

- Incidence of TEAEs leading to death
- Incidence of treatment-emergent SAE by SOC and PT
- Incidence of treatment-related treatment-emergent SAE by SOC and PT

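### The worsening branch of the TEAE definition lacks the 28-day post-dose window of the other two branches, so read literally, late worsening of a pre-existing condition drops out of the AE summary tables

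*SAP*

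**What the plan says.** SAP Section 5.6.2 gives three routes by which an adverse event becomes treatment-emergent:

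- Branch 1, new event: "emerges during treatment (up to 28 days after the last dose of study drug), having been absent at pretreatment (Baseline").
- Branch 2, returning event: "Reemerges during treatment (up to 28 days after the last dose of study drug), having been present at pretreatment (Baseline) but stopped before treatment".
- Branch 3, worsening event: "Worsens in severity during treatment relative to the pretreatment state, when the AE is continuous".

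The 28-day extension is written out in branches 1 and 2. It does not appear in branch 3.

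The same section then fixes what is reported where. For tables: "Only those AEs that were treatment emergent will be included in summary tables". For listings: "All AEs, treatment emergent or otherwise, will be presented in subject data listings". The tables include treatment-emergent SAEs by system organ class and preferred term, and TEAEs leading to death.

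**The concern.** The three branches should share one time window, because they feed the same counts. As written, two events on the same day after the last dose can be treated differently only because one subject already had the condition at baseline. The subjects affected are those with a chronic or recurring condition, for whom deterioration during or just after treatment is what a safety table should show. Section 3.1.3 names depression and suicidal ideation or behavior among the safety assessments, and depression is a condition that can be present at baseline and then worsen.

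The restriction reaches the SAE and fatal-event tables too. Under the literal wording, a pre-existing condition that first deteriorates to a serious or fatal outcome shortly after the last dose would be in neither. Efficacy is now descriptive only (Section 7), so the safety tables carry more of the report's weight.

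**Working it through.** The SAP states no figure to reproduce. The check sets each pattern of onset, resolution and worsening against the three branches in Section 5.6.2.

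| Pattern | Branch met | TEAE? |
|---|---|---|
| (a) New event, on drug or 1–28 days after last dose | 1 | Yes |
| (b) Present at baseline, stopped before first dose, returns on drug or 1–28 days after last dose | 2 | Yes |
| (c) Continuous from baseline, worsens while on drug | 3 | Yes |
| (d) Continuous from baseline, first worsens 1–28 days after last dose | None if branch 3 is read literally; 3 if the 28-day gloss is carried over | Depends on the reader |
| (e) Ongoing at first dose, resolves on drug, recurs at same or lower severity | None | No |
| (f) Ongoing at first dose, resolves on drug, recurs at higher severity | Not 1 (present at baseline), not 2 (did not stop before treatment), 3 doubtful (not continuous) | Unclear |

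Pattern (d) is the main gap. Compare it with (a): on the same post-dose day, the new event counts and the worsening does not.

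Pattern (f) is the secondary gap. Branch 2 requires "having been present at pretreatment (Baseline) but stopped before treatment, or" and branch 3 requires the event to be continuous, so a worse recurrence after resolution on treatment falls between them.

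Size of the window in (d), where D is the study day of the last dose:

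- Window for branches 1 and 2: Day 1 to D + 28.
- Window for branch 3, read literally: Day 1 to D.
- Uncounted share = 28 / (D + 28).

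The values of D are assumptions, taken from the target days for Weeks 12 and 52 in the windowing table of Section 8.1.1:

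- D = 84: 28 / (84 + 28) = 28 / 112 = 25%.
- D = 364: 28 / (364 + 28) = 28 / 392 = 7.1%.

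These are shares of time, not of events. The SAP gives no count of baseline conditions or of worsening events, so no count of missing TEAEs can be derived.

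**The case against.** The strongest reply on the window is that branches 1 and 2 gloss the phrase on treatment time as extending 28 days past the last dose, and branch 3 uses the same phrase in the same definition. Carrying the gloss over is a natural reading, and this part of the objection stands: the exclusion in (d) is what the literal text gives, not a certainty. But the SAP does not secure the kinder reading. If the first gloss defined the phrase throughout, repeating it in branch 2 would be needless. Elsewhere the boundary differs: Section 5.6.1 ends exposure at the last dose, and the end-of-treatment window in Section 8.1.1 refers to the last dose plus 14 days. Two programmers could produce different tables from the same data. Section 9 leaves derivation rules to separate documents, which may settle the matter, but the definition itself is set in the SAP.

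Several stronger inferences are tempting and are not supported:

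- *A baseline condition that returns on drug is never counted.* Branch 2 covers such a condition if it stopped before treatment, and carries the 28-day window. Only conditions still ongoing at first dose are in question.
- *Every recurrence ought to count.* Whether a recurrence at the same or lower severity (pattern e) is treatment-emergent is a definitional choice, not an error.
- *The events vanish from the report.* They remain in the listings. Depression is also a separate safety analysis in Section 5.6.6 that does not depend on TEAE status.
- *A quarter of worsening events is lost.* The 25% is a share of time at one assumed stopping day.
- *Early termination creates the problem.* Completers also have a period after the last dose. Shorter treatment only makes the 28 days a larger share of the window.

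Section 5.6 rules out hypothesis testing for safety, so no inferential result is affected.

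**Conclusion.** The concern holds in limited form. The TEAE definition is inconsistent across its three branches. Followed to the letter, it omits from the AE, SAE and fatal-event summary tables any continuous pre-existing condition that first worsens in the 28 days after the last dose. A worse recurrence after resolution on treatment has no clear place.

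The main point assumes that branch 3 is applied as written and that no unseen programming document overrides it. The gap is 28 days per subject, or about 7% to 25% of the TEAE window for a last dose between Day 364 and Day 84, with a larger share for earlier stops. The number of events is unknown and may be small. The correction should be made because it is cheap and removes an arbitrary difference in how safety events are counted.

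**What to change.** Reword branch 3 in Section 5.6.2 in two respects:

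1. State the same limit of 28 days after the last dose that branches 1 and 2 carry, directly after the reference to treatment.
2. Keep the condition that the event be continuous, and add an alternative: or when the event resolves during treatment and recurs at greater severity.

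Branch 2 can stay as it is. Recurrences at the same or lower severity then remain outside the TEAE definition, and it would help to say so in one sentence so that the choice is explicit.

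The cost is one reworded branch in the SAP and a matching change to the TEAE derivation. TEAE counts may rise slightly in both arms, and the rule applies to both arms alike.

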3 INTRODUCTION

The purpose of this statistical analysis plan (SAP) is to describe the procedures and the statistical methods that will be used to analyze and report results for Eisai Protocol APD356-A001-403.

Since this study has been terminated early and when only about 20% of subjects have completed week 52 visit, many of the planned efficacy outputs will not show enough data as initially planned for this study. Most planned efficacy tables will not be produced. For details on changes in planned analysis, please see section 7 “Changes in Planned Analysis”.

This document is prepared based on the final study protocol (protocol V10.0 12Feb2018). Reader is referred to the final study protocol, the case report form (CRF), general CRF completion guidelines for details of study design, conduct and data collection.

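### TEAEs are reported only as crude percentages although few subjects reached Week 52, so the tables have no stated time base; the exposure definition also drops the first dosing day

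*SAP*

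**What the plan says.** **Adverse events.** Section 5.6.2 lists the TEAE and SAE summaries, and each is an incidence, for example "Incidence of TEAEs by SOC and PT". The counting rule is "A subject will be counted only once within a SOC or PT", which applies when a subject has several events. Section 5.6 calls for descriptive statistics or frequency counts by treatment group, without hypothesis tests, and sections 5 and 5.3.6 present categorical data as counts and percentages. No person-time denominator, exposure-adjusted rate or time-to-event summary appears. An event counts as treatment-emergent up to 28 days after the last dose.

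**Follow-up.** Section 3 opens its account of the early stop with "Since this study has been terminated early and when only about 20% of subjects have completed week 52 visit". Section 7 lists five changes made because of termination; none concerns adverse events or exposure.

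**Exposure.** Section 5.6.1 states "Subjects will receive Belviq XR 20 mg or placebo QD for up to 52 weeks" and sets the length of exposure in these terms: "number of weeks between the date the subject received the 1st dose of study drug and the date the subject received the last dose". It is summarised by arm, with descriptive statistics and in categories whose limits are not given. Section 5.6 sets the day count: "Study Day 1 for all safety analyses will be defined as the date of the 1st dose of study drug". Table 1 in section 8.1.1 puts the Week 52 target at Day 364.

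**The concern.** A percentage of subjects with an event is a risk over some period. If nearly everyone is followed for 52 weeks, the period is understood. Here roughly 80% had not completed Week 52, so the period is an unstated mix of durations. Section 3.2 keeps subjects in the study after they stop treatment, but that does not restore a common period for TEAEs, because the window ends 28 days after the last dose.

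Efficacy has been cut back to simple descriptive summaries, so safety is the main remaining product of the trial. A reader who takes the percentages as results of a 52-week trial, or sets them beside completed 52-week trials, would understate the risk in both arms.

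The exposure definition raises a smaller, separate point. Weeks counted between two dates leave out one of the two end days, whereas the SAP otherwise numbers the first dosing day as Day 1. The Safety Analysis Set (section 5.2.1) can include a subject with a single dose.

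**Working it through.** The SAP states no event rate, event count or person-time, so there is no planned figure to reproduce, and actual exposure-adjusted rates cannot be computed. The check asks how far the crude percentage can move when only follow-up changes.

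**1. Crude percentage against follow-up**

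From the SAP: about 20% completed Week 52 (section 3); treatment lasts up to 52 weeks (section 5.6.1); the TEAE window runs to last dose + 28 days (section 5.6.2).

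Assumed: a constant first-event rate λ per subject-year, and two patterns for the other 80%. In pattern A their time on drug is spread evenly over 0.5 to 52 weeks. In pattern B they all stop at 12 weeks.

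Formula: crude percentage = mean over subjects of 1 − exp(−λ × weeks/52), ignoring the 28-day window at first.

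| λ | All at 52 weeks | Pattern A | Pattern B |
|---|---|---|---|
| 0.2 | 18.1% | 11.2% | 7.2% |
| 0.5 | 39.3% | 25.1% | 16.6% |
| 1.0 | 63.2% | 42.3% | 29.1% |

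Worked cell, λ = 0.5, pattern B: 0.8 × (1 − exp(−0.5 × 12/52)) + 0.2 × (1 − exp(−0.5)) = 0.8 × 0.109 + 0.2 × 0.393 = 16.6%.

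Relative to full follow-up, the same rate gives 62% to 67% of the percentage in pattern A and 40% to 46% in pattern B.

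Adding the 28-day window gives every subject 4 more weeks and narrows the gap a little. For λ = 0.5, full follow-up becomes 1 − exp(−0.5 × 56/52) = 41.6%. Pattern B becomes 0.8 × (1 − exp(−0.5 × 16/52)) + 0.2 × 0.416 = 0.8 × 0.143 + 0.083 = 19.7%, still under half.

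**2. Between arms**

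With the same λ and the same follow-up, the two percentages are equal. With λ = 0.5 in both arms and an assumed 26 weeks in each, both are 1 − exp(−0.25) = 22.1%. If time on drug were 20 weeks in one arm and 30 in the other (assumed), they would be 1 − exp(−0.5 × 20/52) = 17.5% and 1 − exp(−0.5 × 30/52) = 25.1%, with no difference in rate. The SAP gives no time on drug by arm, so this shows only what would have to be true.

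**3. Exposure definition**

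Literal reading: (last − first)/7. Counting both end days: (last − first + 1)/7.

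| Daily dosing from Day 1 to | Literal | Both days counted | Shortfall |
|---|---|---|---|
| Day 1 | 0 weeks | 0.14 | 100% |
| Day 7 | 0.86 | 1.00 | 14% |
| Day 84 | 11.86 | 12.00 | 1.2% |
| Day 364 | 363/7 = 51.86 | 364/7 = 52.00 | 0.3% |

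The loss is always one day. It matters only for very short exposures and at category boundaries: a subject dosed to the Day 364 target would fall short of any category that begins at 52 weeks.

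**The case against.** The SAP nowhere calls these figures 52-week incidences. It promises descriptive safety summaries without tests, and nothing in it is contradicted by using crude percentages. It also reports exposure by arm, so a reader can see whether the arms differ in time on drug. On this view the extra rates are an optional analysis in a plan deliberately reduced after termination. Much of this stands: the point is an improvement to the plan and does not correct a false statement. The exposure table still does not give the event percentages a time base, because a rate needs each subject's time to first event, which cannot be recovered from two marginal tables.

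A reader might infer that the crude percentages bias the comparison between arms. The documents do not support that. Randomisation is 1:1 and double-blind, and a study-wide stop should shorten both arms alike. One can construct a gap: with a rate of 1 per subject-year and 0.55 against 0.45 years, 1 − exp(−0.55) = 42.3% and 1 − exp(−0.45) = 36.2%, about 6 points. Those times are assumed, and the calculation gives every subject in an arm the same follow-up. With a rarer event at an assumed 0.05 per subject-year, the same times give 2.7% against 2.2%. The 6 points are an illustration and not an artefact to be expected.

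The phrase very unequal follow-up is likewise an inference from the 20% figure. Part of the non-completion may be ordinary dropout, for which section 4 allowed 40%.

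On exposure, the loss is one day in each arm and cancels in a comparison. Section 9 leaves derivation rules to separate documents, so the programs may already count both days. That makes the point minor, but the definition given in the SAP should still be right as written.

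**Conclusion.** The point holds in a limited form. The planned TEAE percentages describe risk over a mixed, shortened period and cannot be read as 52-week incidences. Under assumed constant rates of 0.2 to 1.0 per subject-year and the two assumed patterns, ignoring the 28-day window, they come out at roughly 40% to 67% of the full-follow-up figure. The true size is unknown because the SAP gives no follow-up distribution. Distortion between arms is conditional on a difference in time on drug, which the SAP does not show.

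The exposure wording is a minor inconsistency with the SAP's own day count: one day per subject, or 0.14 week. Adding rates is a cheap improvement worth making. Its absence does not invalidate the planned tables.

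**What to change.** Keep the crude percentages. Beside them, in section 5.6.2, add the number of subjects with the event per 100 subject-years for:

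- overall TEAEs;
- treatment-emergent SAEs;
- the more common SOCs and PTs, with the frequency cut-off stated in advance.

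Define time at risk as running from first dose to the earliest of first event, last dose + 28 days, or last contact. State in a footnote that the percentages are not 52-week risks, and add the change to section 7.

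In section 5.6.1, define duration of exposure as (last dose date − first dose date + 1)/7 weeks.

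The cost is one more column in the chosen tables and a time-to-first-event derivation for each reported term, using dose, event and last-contact dates. The drawback is that a rate per subject-year assumes a roughly constant rate. If events cluster soon after the start of treatment, it can mislead, which is why the percentages should stay beside it.

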5.6.3 Laboratory Values

Laboratory results will be summarized using standard international units, as appropriate. For all quantitative parameters, the actual value and the change from baseline to each post baseline visit and to the end of treatment (defined as the last on-treatment value) will be

summarized by visit and treatment group using descriptive statistics. Percentages will be based on the number of subjects with both no missing baseline and relevant post baseline results.

Laboratory test results will be assigned a low/normal/high (LNH) classification according to whether the value was below (L), within (N), or above (H) the laboratory parameter's reference range. Within-treatment comparisons for each laboratory parameter will be based on 3-by-3 tables (shift tables) that compare the baseline LNH classification to the LNH classification at the End of Treatment and the Follow-Up visits. Similar shift tables will also compare the baseline LNH classification to the LNH classification for the highest and lowest value during the treatment period.

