- To assess the safety of Belviq XR, including the effects on cognition by Leiter-3 International Performance Scale (Leiter-3), depression with the Patient Health Questionnaire (PHQ-9), signal of suicidal ideation or behavior with the Columbia-Suicide Severity Rating Scale (C-SSRS), growth measured by CDC growth chart, sexual maturation (pubescence) measured by Tanner Staging scores, and other growth and development parameters by measuring sex hormones, thyroid function, adrenal function, bone age, and biochemical markers of bone health, bone mineral density and content, total body fat mass and total body lean mass by DEXA in a subset of randomized subjects (selected prior to randomization) at selected sites, valvular function, pulmonary arterial pressure.
 - To assess the pharmacokinetic (PK) of lorcaserin using population PK modeling
 - To assess relationships between plasma exposure to lorcaserin and pharmacodynamics (PD) parameters including but not limited to reduction from baseline in BMI and probability of achieving at least a 5% and at least a 10% reduction in BMI from baseline at Week 52 using population PK/ PD modeling

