3.2 Overall Study Design

This is a multicenter, randomized, double-blind, placebo-controlled, parallel-group study in obese adolescents ages 12 to 17 years. Approximately 260 subjects will be randomized in a 1:1 ratio to Belviq XR 20 mg QD (130 subjects) and placebo (130 subjects). Subjects will be stratified by sex. Subjects will receive Belviq XR 20 mg or matched placebo QD in a 1:1 ratio for up to 52 weeks. A recruitment plan will be developed to ensure at least 20% of younger subjects (12 to 13 years of age) are enrolled in the study.

Throughout the duration of the study, subjects will be encouraged to adhere to a lifestyle modification program that includes a standardized, age-appropriate diet and exercise counseling (see [Appendix 2](#)).

The study will consist of 2 phases: Prerandomization and Randomization. The Prerandomization Phase will last up to 30 days and consists of 1 visit during which subjects will be screened for eligibility. The Randomization Phase consists of a Treatment Period and a Follow-Up Period. The Treatment Period will last for a maximum of 52 weeks, with visits at Weeks 1, 5, 8, 12, 20, 28, 36, 44, and 52; the Follow-Up Period will extend from the End of Treatment (EOT) visit to the End of Study (EOS) visit.

Subjects who screen fail can be rescreened only once. All subjects will continue in the study until the 52-week evaluation is completed. Subjects who discontinue treatment prematurely will be followed up until study completion. All attempts will be made to capture height and weight in all subjects whether or not they are still on study drug at the end of the study.

Details of the study procedures and schedule of assessments can be found in Table 2 of the protocol.

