5.3.6 Other Considerations

Due to the early termination of the study, only simple summary of descriptive statistics will be provided for efficacy endpoint.

Individual subject data in the database will be presented in data listings.

The following rules/definitions will be applied in the final outputs:

- Homeostatic Model Assessment of Insulin Resistance (HOMA-IR Fasting insulin (mIU/L) x Fasting glucose (mmol/L) / 22.5)
- Dyslipidemia: Please use the following link: (https://www.nhlbi.nih.gov/files/docs/peds_guidelines_sum.pdf) and consider subject “with Dyslipidemia” if TC \geq 170 or LDL-C \geq 110 or Non- HDL-C \geq 120 or TG \geq 90 or HDL-C \leq 40. Values given are in mg/dL. **To convert to SI units, divide the results for total cholesterol (TC), low-density lipoprotein cholesterol (LDL-C), high-density**

lipoprotein cholesterol (HDL-C), and non-HDL-C by 38.6; for triglycerides (TG), divide by 88.6.

- Prehypertension or Hypertension:

BP is classified as SBP and DBP percentiles for age/sex/height.

Prehypertension: If SBP or DBP $\geq 90^{\text{th}}$ percentile or $< 95^{\text{th}}$ percentile or BP $> 120/80$ mmHG to $< 95^{\text{th}}$ percentile

Hypertension: If SBP or DBP $\geq 95^{\text{th}}$ percentile or BP $\geq 95^{\text{th}}$ percentile

- Subjects who are type 2 diabetes (T2DM) at Baseline are defined as follows:

Positive diagnosis of diabetes (Preferred Term: *Type 2 diabetes mellitus*) based on Medical History Form or AE with the start date prior to the first dose of the study drug.

The formula for BMI is weight in kilograms divided by height in meters squared.

Continuous variables will be summarized using the following descriptive summary statistics: the number of subjects (n), mean, standard deviation (SD), minimum value (min), and maximum value (max). Minimum and maximum values will be reported with the same precision as the units of measure. The mean and median will be reported to 1 greater decimal place, and the SD will be reported to 2 additional decimal places.

Categorical variables will be summarized using counts and percentages. Percentages will be presented to 1 decimal place.

Baseline Value: The baseline value will be defined as the most recent non-missing measurement (scheduled or unscheduled) collected prior to the initial administration of study drug. Unscheduled visit measurements will be included for derivation of baseline.

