5.6.6 Other Safety Analyses

Other safety analyses will include the following:

- Change in puberty status
- Waist circumference
- DEXA Z-score
- Cognition
- Depression
- Valvular function
- Pulmonary pressures

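### Sex hormones are a stated safety objective in adolescent boys and girls, but the laboratory rule pools the sexes; a by-sex summary is a cheap improvement

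*SAP*

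**What the plan says.** SAP 3.2 describes a "parallel-group study in obese adolescents ages 12 to 17 years" and adds "Subjects will be stratified by sex". SAP 3.1.3 includes in the safety objective "other growth and development parameters by measuring sex hormones, thyroid function, adrenal function, bone age", next to Tanner staging.

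SAP 5.6.3 gives one rule for numerical laboratory results: "For all quantitative parameters, the actual value and the change from baseline to each post baseline visit", and to end of treatment, are "summarized by visit and treatment group using descriptive statistics". It also plans shift tables that classify each result as "below (L), within (N), or above (H) the laboratory parameter's reference range". These compare baseline with end of treatment, with follow-up, and with the highest and lowest on-treatment values. It does not say whether the reference ranges depend on sex, age or pubertal stage.

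Two other places bear on the point. SAP 5.3.6 states "Individual subject data in the database will be presented in data listings". SAP 5.6.6 lists "Change in puberty status" among the other safety analyses, without a method and without a link to hormones.

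**The concern.** Sex hormone levels differ between boys and girls and change through puberty. When two groups sit at different levels, a pooled mean, median or SD describes neither. A drug effect in one sex is averaged with the absence of an effect in the other, and effects in opposite directions offset each other.

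At stake is how well the planned tables would show an endocrine signal in adolescents. Sex is the stratification factor, so it is known for every subject and a split needs no new data. The SAP already allows for this kind of dependence elsewhere: 5.3.6 classifies blood pressure by percentiles that take sex into account.

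**Working it through.** **Is there another rule for sex hormones?**
- 5.6.3 does not name sex hormones, but it applies to all quantitative laboratory parameters.
- 5.6.6 does not list them.
- 5.5 leaves biomarker methods to a possible separate plan, and 5.5.2 limits the output to plasma concentrations of lorcaserin.
- The grading table in 13.1 has no sex hormone row.
- The subgroup text in 5.3.4, 5.4.1.3 and section 7 concerns efficacy. It neither supplies nor forbids a by-sex safety table.

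So 5.6.3 is the only rule in the SAP that can apply, and its classifiers are visit and treatment.

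**How much does pooling matter?** The SAP gives no hormone figure to reproduce. The inputs below are assumptions for illustration: testosterone in boys with mean 400 and SD 150 ng/dL, in girls with mean 30 and SD 15, and a share of boys m = 0.4.

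*Actual values.*
- Pooled mean = 0.4 × 400 + 0.6 × 30 = 178, a level typical of neither sex.
- Pooled variance = 0.4 × 150² + 0.6 × 15² + 0.4 × 0.6 × (400 − 30)² = 9,135 + 32,856 = 41,991, so SD = 204.9. The gap between the sexes supplies 32,856 / 41,991 = 78% of this variance.
- If the share of boys at a visit is 50% instead of 40% and no subject changes, the pooled mean is 0.5 × 400 + 0.5 × 30 = 215, a rise of 37 / 178 = 21%.

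*Change from baseline.*
- A fall of 80 in boys and none in girls gives a pooled mean change of 0.4 × (−80) = −32. For m = 0.3 to 0.5 it is −24 to −40.
- The gap in levels cancels within subjects, so the relevant spread is the SD of change. Assume an SD of change of 15 in girls and s = 75 to 150 in boys. The pooled SD of change is √(0.4 s² + 0.6 × 15² + 0.24 × 80²):
  - s = 75: √(2,250 + 135 + 1,536) = 62.6
  - s = 150: √(9,000 + 135 + 1,536) = 103.3
- The standardised effect is then 32 / 62.6 = 0.51 down to 32 / 103.3 = 0.31. In boys alone it is 80 / 75 = 1.07 down to 80 / 150 = 0.53. Pooling therefore keeps roughly half of it.
- In the sex-mix example above no subject changes, so the mean change is 0 at 40% and at 50% boys. Only the actual-value rows move.

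*Opposite effects.* With +0.5 SD in boys and −0.5 SD in girls, the pooled effect is 0.5m − 0.5(1 − m): −0.20 at m = 0.3, −0.10 at m = 0.4 and 0 at m = 0.5.

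**How small would the cells be?** The SAP introduction says that about 20% completed Week 52. If all 260 planned subjects had enrolled, this is 0.20 × 260 = 52 subjects, 26 per arm, and about 13 per arm and sex if the sexes were equal in number. The number actually enrolled is not given.

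**The case against.** The strongest reply is that the pooled tables still answer a question. Randomisation is stratified by sex, so the arms should start with a similar sex mix, and the difference in mean change then estimates a sex-averaged effect. The shift tables work subject by subject; if the reference ranges are specific to sex and age, pooling does not distort them. Listings show every value. This is a terminated study, reduced on purpose to basic descriptives, with no hypothesis tests for safety. The table shells are in a separate document and might already split by sex.

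Much of this stands, and it rules out several stronger readings:
- A reader might infer that the hormone objective becomes uninterpretable. It does not; it becomes less sensitive.
- A reader might divide the pooled change of −32 by the pooled SD of levels, 204.9, and report 0.16 SD. That denominator is mostly the gap between the sexes, which cancels in change from baseline.
- A reader might infer that a drifting sex mix would pass for a drug effect. In the example it moves only the actual-value rows, and a drift common to both arms would not separate drug from placebo. The SAP gives no information on dropout by sex.
- A reader might extend the point to all laboratory parameters. The argument concerns sex hormones.

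What does not stand is reliance on the shells or the listings. Shells should implement the stated rule, and that rule has no split. Listings are not a summary. Shift tables miss movement within the normal range, and the SAP does not say which ranges apply. Stratification balances the sexes at randomisation, not necessarily among those still measured at late visits.

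**Conclusion.** The point holds as a cheap improvement, not as an error that defeats the objective. As written, the plan pools boys and girls for a safety measure that it names as an objective. Under the assumed values, a change in boys only is shown at 40% of its size in the pooled mean change (−32 against −80) and at about half its standardised size (0.31 to 0.51 against 0.53 to 1.07 SD). Opposite changes can cancel, and pooled actual values describe neither sex.

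These sizes depend on the assumed hormone levels, SDs of change and share of boys. The direction needs only that levels, or drug effects, differ by sex. That 5.6.3 governs sex hormones is inferred from its scope, because the section does not name them.

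**What to change.** Add to SAP 5.6.3: *Sex hormones (actual value, change from baseline and low/normal/high shift) will be summarised by sex within treatment group at each applicable visit. Baseline Tanner stage will be shown in the subject listing.*

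The shells should follow. Sex is the stratification factor and Tanner staging is part of the safety objective, so no new data and no tests are needed. The cost is a few extra descriptive tables, with small cells at late visits (about 13 per arm and sex at Week 52 under the assumptions above). A tabulated breakdown by Tanner stage would leave only a handful of subjects per cell, which is why the listing is enough for that variable.
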